4.1.6 Handling of Baseline Differences

Group differences in baseline characteristics will be evaluated. Analyses will be performed to evaluate the treatment effect controlling for baseline covariates found to have clinically meaningful baseline differences. Clinically meaningful will be determined by the Sponsor Study Safety Monitor or Primary Investigator. This will be done using a generalized linear model with parameters estimated using SAS PROC GENMOD with distribution set to *binomial* and link set to *logit*. The adjusted probabilities and their standard errors are determined on the probability scale using the *ilink* option in a *lsmeans* statement with a *diff* option. This statement produces a test for the treatment group difference controlling for other covariates in the model. The model will include treatment group and each identified covariate one-at-a-time. The standard error on the probability scale for the difference in event rates will be determined as the square root of the sum of the treatment group specific squared standard errors and used in the determination of the 95% CI.

As requested by FDA, multivariable analyses will be provided to the degree that sample size and number of observed events in each group allow. It is understood that a total of 10 events per covariate is necessary for this modeling approach, which limits the number of covariates the model can support. The full model will consist of age, BMI, sex, and the number of days since first COVID-19 symptom (≤ 5 or > 5 days), in addition to treatment group (sample size permitting). In addition to the full model, a forward stepwise procedure will be used to identify a set of covariates that each provide some independent association with the primary outcome.

The totality of evidence (i.e., the clinical and statistical interpretations) will provide support for decision making regarding Phase III investigation.

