4.1.3 Testing of Primary Efficacy Hypothesis

Primary results will include the numbers and percentages of subjects in each treatment group requiring COVID-19 related hospitalization/ER visit or who died due to any cause within 28 days of randomization.

As noted in the next section, the study is statistically powered by assuming that $\pi_{cm} = 0.15$ and $\pi_{pl} = 0.30$ and the number of subjects to be randomized are 186 and 93, in the active and placebo arms, respectively. Consequently, the expected number of subjects to experience the event is nearly 28 for both arms, with 158 and 65 subjects in the active and placebo arms, respectively, not expected to experience the primary endpoint. Therefore, an unadjusted chi-squared test (or exact test, if expected cell counts are < 5 in either group) will be used to test the primary efficacy hypotheses using a two-sided type 1 error of 0.05. Superiority will be concluded if $p < 0.05$ and the proportion of subjects experiencing the event is smaller among subjects randomized to the active treatment. This is tantamount to specifying a one-sided type 1 error rate of $\alpha = 0.025$.

In addition to determining the p-value for the primary efficacy hypothesis, results will also be expressed in terms of a two-sided normal based (asymptomatic) 95% confidence interval estimating the treatment group difference in 28-day COVID hospitalization or death. The upper bound of the confidence interval will be interpreted as the smallest treatment effect consistent with the study results.

If the expected number of events in either group is less than five (5), a Fisher's exact test and exact binomial intervals will be provided.

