4.1.4 Sample Size Determination for the Primary Efficacy Hypothesis

Sample size determination assumed event rates of 15% and 30% in the active and placebo groups, respectively, 2:1 randomization, and a two-sided type 1 error rate of $\alpha=0.05$. Under these assumptions, an adjusted chi-square test will have 80% power for sample sizes of 186 and 93 in the investigational and placebo arms, respectively (total sample size = 279). The sample size is increased by approximately 7.5% to allow for up to 200 and 100, respectively, to account for loss-to-follow-up.

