[figure not shown]
	Number and Percentage with Endpoint						p-value ²	Difference and Confidence Interval (%) ³		
	Camostat mesilate			Placebo				Diff.	LB	UB
Hospitalization/ER visit or death within 28 Days	N	n	%	N	n	%				
Adjusted for baseline covariates with clinically significant group differences ⁴										
Adjusted for all covariates ⁵										
Model identified by stepwise ⁶										

Notes:
 
¹ The Intent-to-Treat (ITT) population will include all subjects who are randomized. Subjects will be analyzed according to their study treatment assignment, not according to the treatment actually received (N=295).
 
² Unadjusted chi-square test
 
³ Two-sided 95% CI
 
⁴ Variable list
 
⁵ Variable list
 
⁶ Variable list
 
Program Source [xxxxxxx.sas]
										

**DRAFT Table 14.2.3
Time to Resolution of Fever
Intent-To-Treat Population**

Interval	Pts at start	#with event	Censored	Cumulative Resolution Rate	SE[‡]
At Start					
Day 1					
...					
Day 14					
Notes: [‡] SE Errors computed using the Peto method. No subjects died on or before Day14. Program source:					

Programming Notes: Time to Resolution of New Fever will be displayed in a similar manner.

**DRAFT Figure 14.2.4
Kaplan-Meier Time to Resolution of Fever
Intent-to-Treat Population**

Program Name: XXXXXX.sas

Database lock date: 17JAN2020; Run Date: 30MAR2021

Note: This figure will include a number At-Risk Table detailing the number of subjects with events and censored for each day of the analysis. Day 0 will be included displaying the number of subjects in the analysis overall.

Programming Notes: Kaplan-Meier Time to COVID-19 Hospitalization/ER visit will be displayed in similar manner.

DRAFT Table 14.2.5
Time to COVID-19 Hospitalization/ER visit or Death
Intent-To-Treat Population

Interval	Pts at start	#with event	Censored	Cumulative Rate	SE[‡]
At Start					
Day 1					
...					
Day 28					

Notes: [‡] SE Errors computed using the Peto method. Program source:
					

**DRAFT Table 14.2.8.1
Shift Table of Fever Severity Categories by Study Day and Treatment**

		Camostat mesilate											Placebo												
		(N=xxx)											(N=xxx)												
		None		Grade 1		Grade 2		Grade 3		Grade 4		Missing		None		Grade 1		Grade 2		Grade 3		Grade 4		Missing	
Study Day		n	%	n	%	n	%	n	%	n	%	n	%	n	%	n	%	n	%			n			%
Day 0	--	xx	xx.x	xx	xx.x	xx	xx.x	xx	xx.x	xx	xx.x	xx	xx.x	xx	xx.x	xx	xx.x	xx	xx.x	xx	xx.x	xx	xx	xx.x	xx.x

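### SAP 4.1.6 back-transforms logit LS-means to get the adjusted risks, so the adjusted difference need not estimate the randomized-population risk difference, even with balanced arms

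*SAP*

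**What the plan says.** SAP 4.1.2 defines the target as the difference in event probability between subjects randomized to camostat and to placebo. SAP 4.1.3 reports the unadjusted result as a 95% interval "estimating the treatment group difference in 28-day COVID hospitalization or death".

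SAP 4.1.6 adds adjusted analyses from a binomial model with logit link in PROC GENMOD. "The adjusted probabilities and their standard errors are determined on the probability scale using the" inverse-link option of an LS-means statement, with a difference option. No other option is named, and the SAP does not say which covariates are CLASS variables. Three sets of models are planned:

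- one covariate at a time, for covariates judged to differ at baseline;
- a multivariable model: "The full model will consist of age, BMI, sex, and the number of days since first COVID-19 symptom" (five days or fewer versus more than five), plus treatment;
- a forward stepwise model.

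Draft Table 14.2.1.4 puts these results in rows such as "Adjusted for baseline covariates with clinically significant group differences". Its title and its percentage, difference and confidence-bound columns are those of the primary Table 14.2.1.1.

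**The concern.** By default, an LS-mean sets continuous covariates at their means and gives each level of a CLASS covariate equal weight. The inverse link is then applied once, to that single linear predictor. This yields the risk of a constructed subject, for example half male and half with more than five symptom days if both factors are CLASS variables. It is not the average risk of the subjects who were randomized.

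The adjusted and unadjusted tables can then disagree although nothing is unbalanced. SAP 4.1.6 exists to show whether baseline differences explain the treatment effect, so a reader would naturally take such a gap as a sign of imbalance. The section says that FDA requested the multivariable results and that the totality of evidence will inform the Phase III decision. Because the coding and the margins are not stated, the reported figure would also depend on a programmer's default.

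**Working it through.** **The plan's own figure.** SAP 4.1.6 gives no figure for the adjusted difference. The inputs come from SAP 4.1.4: "Sample size determination assumed event rates of 15% and 30% in the active and placebo groups, respectively, 2:1 randomization", and "an adjusted chi-square test will have 80% power for sample sizes of 186 and 93 in the investigational and placebo arms, respectively". At 186/93, exact power is 78.9% for the continuity-corrected chi-square, 80.2% for Fisher's test and 83.0% for the uncorrected Pearson test, so the stated 80% is reproduced. The inflation also checks: 279 × 1.075 = 300.

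**Set-up.** Take balanced arms with average risks of exactly 30% (placebo) and 15% (camostat), so the true difference is -15.0 points. Add one two-level covariate. The split q (share at the higher-risk level) and the odds ratio OR are assumptions, because the documents give neither. In each arm, with b = ln(OR), solve for the intercept a:

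(1 - q) × expit(a) + q × expit(a + b) = average risk.

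Then compare three estimates of the difference:

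- default LS-means: expit(a + 0.5b) in each arm;
- covariate at its observed mean: expit(a + qb) in each arm;
- standardization: the left side of the equation above.

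**One case in full: q = 0.20, OR = 2, b = 0.693.**

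- Placebo: a = -1.000. The level risks are 26.9% and 42.4%, and 0.8 × 26.9 + 0.2 × 42.4 = 30.0%.
- Camostat: a = -1.901. The level risks are 13.0% and 23.0%, and 0.8 × 13.0 + 0.2 × 23.0 = 15.0%.
- Default LS-means: expit(-0.653) = 34.2% and expit(-1.555) = 17.4%. The difference is -16.8 points, and 16.79/15.0 = 1.119, so it is about 12% too large.
- At the observed mean: 29.7% and 14.65%, difference -15.06 points.
- Standardized: -15.0 points.

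**Range** (camostat minus placebo, in points; the truth is -15.0):

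| OR | q | Default LS-means | Error | At observed mean |
|---|---|---|---|---|
| 1.5 | 20% | -16.0 | +6.8% | -15.0 |
| 1.5 | 80% | -14.0 | -6.7% | -15.0 |
| 2 | 50% | -15.0 | +0.1% | -15.0 |
| 2 | 20% | -16.8 | +11.9% | -15.1 |
| 2 | 80% | -13.25 | -11.7% | -15.0 |
| 3 | 20% | -18.0 | +20.0% | -15.2 |
| 3 | 80% | -12.1 | -19.0% | -14.9 |

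**Two sources, separated.** The last column shows that evaluating risk at the mean covariate moves the difference by at most 1.5% at these rates. For a continuous covariate with logit-scale SD of 0.3 to 1.0, the error is +0.2% to +0.7%. Nearly all of the error in the difference therefore comes from the 50:50 weighting. The arm risks are more sensitive: with a covariate score of SD 1 on the logit scale they fall from 30% and 15% to 26.5% and 11.4%, while the difference is -15.1.

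**Scale.** At 200/100 the standard error of the unadjusted difference is √(0.30 × 0.70/100 + 0.15 × 0.85/200) = 5.2 points. The OR 2 shift of about 1.8 points is roughly one third of that.

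**The case against.** The strongest reply is that 4.1.6 promises only an effect controlling for covariates, which is a legitimate conditional summary. The results sit in a separate draft table with rows labelled as adjusted, and the SAP says its shells may be revised. The 50:50 weighting depends on CLASS coding, which the SAP does not state. A 0/1 covariate entered as numeric is set at its mean, and the error in the difference almost vanishes. Only two of the four full-model covariates are two-level, and no split is documented for either; near 50:50 there is no practical error.

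Most of this stands, and it limits the point to a possible error of unknown size. It does not remove the point. SAP 4.1.2 and 4.1.3 define the effect over randomized subjects, the adjusted table uses the same columns, and the weighting is left open.

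Three stronger readings are tempting, and the documents do not support them:

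- *The adjusted effect is off by 12%.* That is one assumed case (OR 2, 20/80 split). It is neither a bound nor an expected value.
- *The average-subject nonlinearity is the main fault.* At the planned rates it barely moves the difference.
- *The error is about 25% if events are rarer.* With 10% versus 5% and a logit SD of 1, observed margins give -3.8 instead of -5.0 points. But 100 × 0.10 + 200 × 0.05 = 20 events. Under the SAP's rule of 10 events per covariate, that supports two covariates, so the four-covariate model would not be run. With SD 0.5 the value is about -4.6 to -4.7, roughly 7% to 9% too small.

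**Conclusion.** The point holds as a defect of the supportive adjusted analyses. As written, SAP 4.1.6 does not estimate the risk difference among randomized subjects, and its result can depart from it in either direction with balanced arms. At 30% versus 15%, with one two-level CLASS covariate and default margins, the error runs from about zero at a 50:50 split to about 7%, 12% and 20% at a 20/80 split with odds ratios of 1.5, 2 and 3. With covariates at their observed means it is under about 2%, although the arm percentages can still be several points low. These sizes rest on assumed splits and effects.

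A reader might infer that the trial's primary conclusion is at risk. It is not: the primary test and its risk difference are unadjusted, and the model's treatment test is on the logit scale. The affected items are the adjusted percentages, differences and confidence intervals.

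**What to change.** Keep the logistic models in SAP 4.1.6 and replace the inverse-linked LS-means with standardization. From each fitted model, predict every subject's risk once under camostat and once under placebo. Average each set over all subjects in the analysis set, and report the difference of the two averages. Give it a delta-method or bootstrap 95% CI in place of the section's root-sum-of-squares standard error, which omits the covariance between the two arm estimates. Apply the same change to PP1 and PP2, and say in the footnotes of the adjusted tables that the risks are standardized.

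In the worked cases this returns -15.0 points whatever the split or odds ratio. Requesting observed margins would be a smaller step that repairs the weighting, but it leaves the arm percentages off when covariates are strong.

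The cost is one paragraph of SAP text and a short program, slightly more work than an LS-means statement. No new data are needed.

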5 APPENDIX: SHELL TABLES AND FIGURES

This section displays mock-ups of the tables, listings, and figures that will be provided in the clinical study report.

SAP TLF's are provided to describe data presentations including examples of the Tables, Listings, and Figures.

The following is a DRAFT set of Tables, Listings, and Figures. Table numbers, layouts, and units are subject to revision.

Table 2: Listing of Tables, Listings, and Figures

TLF Name	TLF Number	Population
Accounting		
Table 14.1.1 - Subject Disposition by Treatment	Table 14.1.1	ITT
Figure 14.1.1 – Subject Disposition by Treatment – Consort Diagram	Figure 14.1.1	ITT
Baseline Demographics		
Table 14.1.2.1 - Summary of Demographic Characteristics by Treatment	Table 14.1.2.1	ITT
Table 14.1.2.2 - Summary of Demographic Characteristics by Treatment	Table 14.1.2.2	PP1
Table 14.1.2.3 - Summary of Demographic Characteristics by Treatment	Table 14.1.2.3	PP2
Table 14.1.2.4 - Summary of Demographic Characteristics by Treatment	Table 14.1.2.4	SP
Table 14.1.3 - Summary of Baseline Clinical Laboratory Data by Treatment	Table 14.1.3	ITT
Table 14.1.4 - Summary of Baseline Vital Signs by Treatment	Table 14.1.4	ITT
Primary/Secondary		
Table 14.2.1.1 - Primary Efficacy – Proportion of Subjects Requiring COVID-19 Hospitalization/ER visit	Table 14.2.1.1	ITT
Table 14.2.1.2 - Secondary Efficacy – Proportion of Subjects Requiring COVID-19 Hospitalization/ER visit	Table 14.2.1.2	PP1
Table 14.2.1.3 - Secondary Efficacy – Proportion of Subjects Requiring COVID-19 Hospitalization/ER visit	Table 14.2.1.3	PP2
Table 14.2.1.4 – General Linear Model of COVID-19 Hospitalization/ER visit Adjusted by Covariates	Table 14.2.1.4	ITT
Table 14.2.1.5 – General Linear Model of COVID-19 Hospitalization/ER visit Adjusted by Covariates	Table 14.2.1.5	PP1
Table 14.2.1.6 – General Linear Model of COVID-19 Hospitalization/ER visit Adjusted by Covariates	Table 14.2.1.6	PP2
Table 14.2.1.7 – Forest Plots of Group Difference in Primary Endpoint with 95% Confidence Intervals Stratified by Categorical Baseline Characteristics	Table 14.2.1.7	ITT
Table 14.2.1.8 – Forest Plots of Group Difference in Primary Endpoint with 95% Confidence Intervals Stratified by Categorical Baseline Characteristics	Table 14.2.1.8	PP1
Table 14.2.1.9 – Forest Plots of Group Difference in Primary Endpoint with 95% Confidence Intervals Stratified by Categorical Baseline Characteristics	Table 14.2.1.9	PP2

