Age Group 2	<65 Years	xxx	xx.x	xxx	xx.x	xxx	xx.x
	>=65 Years	xxx	xx.x	xxx	xx.x	xxx	xx.x
Age Group 3	<75 Years	xxx	xx.x	xxx	xx.x	xxx	xx.x
	>=75 Years	xxx	xx.x	xxx	xx.x	xxx	xx.x
Time from Positive Covid-19	<= 5 days	xxx	xx.x	xxx	xx.x	xxx	xx.x
Test to Randomization	>5 days	xxx	xx.x	xxx	xx.x	xxx	xx.x
Race	White	xxx	xx.x	xxx	xx.x	xxx	xx.x
	Black or African American	xxx	xx.x	xxx	xx.x	xxx	xx.x
	Asian	xxx	xx.x	xxx	xx.x	xxx	xx.x
	Native American or Alaska Native	xxx	xx.x	xxx	xx.x	xxx	xx.x
	Native Hawaiian or Other Pacific Islander	xxx	xx.x	xxx	xx.x	xxx	xx.x
	Multi-racial	xxx	xx.x	xxx	xx.x	xxx	xx.x
	Unknown	xxx	xx.x	xxx	xx.x	xxx	xx.x
Race Group 1 ^a	White	xxx	xx.x	xxx	xx.x	xxx	xx.x
	Non-White	xxx	xx.x	xxx	xx.x	xxx	xx.x

DRAFT Table 14.1.2.1.1
Summary of Categorical Demographic Characteristics by Treatment
Intent-to-Treat Population

Ethnicity	Hispanic or Latino	xxx	xx.x	xxx	xx.x	xxx	xx.x
	Not Hispanic or Latino	xxx	xx.x	xxx	xx.x	xxx	xx.x
	Unknown	xxx	xx.x	xxx	xx.x	xxx	xx.x
Risk Factors	Age 65 or Older	xxx	xx.x	xxx	xx.x	xxx	xx.x
	Chronic Cardiac Conditions	xxx	xx.x	xxx	xx.x	xxx	xx.x
	Chronic Liver Disease	xxx	xx.x	xxx	xx.x	xxx	xx.x
	Chronic Lung Disease	xxx	xx.x	xxx	xx.x	xxx	xx.x
	Diabetes Mellitus	xxx	xx.x	xxx	xx.x	xxx	xx.x
Risk Factors	Hypertension	xxx	xx.x	xxx	xx.x	xxx	xx.x
	Severe Obesity	xxx	xx.x	xxx	xx.x	xxx	xx.x
Number of Risk Factors	1	xxx	xx.x	xxx	xx.x	xxx	xx.x
	2	xxx	xx.x	xxx	xx.x	xxx	xx.x
	3	xxx	xx.x	xxx	xx.x	xxx	xx.x
	4	xxx	xx.x	xxx	xx.x	xxx	xx.x
	5	xxx	xx.x	xxx	xx.x	xxx	xx.x
	6	xxx	xx.x	xxx	xx.x	xxx	xx.x
Northeast	Site xxx	xxx	xx.x	xxx	xx.x	xxx	xx.x
	Site ...	xxx	xx.x	xxx	xx.x	xxx	xx.x
	Site xxx	xxx	xx.x	xxx	xx.x	xxx	xx.x
South	Site xxx	xxx	xx.x	xxx	xx.x	xxx	xx.x
	Site ...	xxx	xx.x	xxx	xx.x	xxx	xx.x

DRAFT Table 14.1.2.1.1
Summary of Categorical Demographic Characteristics by Treatment
Intent-to-Treat Population

	Site xxx	xxx	xx.x	xxx	xx.x	xxx	xx.x
West	Site xxx	xxx	xx.x	xxx	xx.x	xxx	xx.x
	Site ...	xxx	xx.x	xxx	xx.x	xxx	xx.x
	Site xxx	xxx	xx.x	xxx	xx.x	xxx	xx.x
Central	Site xxx	xxx	xx.x	xxx	xx.x	xxx	xx.x
	Site ...	xxx	xx.x	xxx	xx.x	xxx	xx.x
	Site xxx	xxx	xx.x	xxx	xx.x	xxx	xx.x

Note: Denominator for percentages is the number of subjects in the intent-to-treat population for a group. *Subjects who did not report a race are not counted in Race Group 1.
 
Program Source: xxxxx.sas Database Lock Date: DDMMMYYYY : Run Date: DDMMMYYYY
							

DRAFT Table 14.1.2.1.2
Summary of Continuous Demographic Characteristics by Treatment

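### SAP 4.1.6 omits the covariance from the standard error of the adjusted risk difference, so the supportive adjusted 95% CIs can be mis-sized and disagree with their p-values

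*SAP*

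**What the plan says.** SAP 4.1.6 plans covariate-adjusted analyses of the primary endpoint with a binomial, logit-link model in PROC GENMOD. Both adjusted probabilities and their standard errors come from one lsmeans statement, transformed to the probability scale. Of the same statement the SAP says: "This statement produces a test for the treatment group difference controlling for other covariates in the model". The model form is then fixed: "The model will include treatment group and each identified covariate one-at-a-time". The standard error of the risk difference "will be determined as the square root of the sum of the treatment group specific squared standard errors" and is "used in the determination of the 95% CI".

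The next paragraph adds a full model (treatment, age, BMI, sex, symptom days) and a stepwise model, and gives no standard-error rule for either. Draft shell Table 14.2.1.4 puts all three kinds of adjusted result under the same p-value and CI columns, starting with the row "Adjusted for baseline covariates with clinically significant group differences". Its p-value footnote reads "Unadjusted chi-square test". SAP Table 2 lists the output, titled "General Linear Model of COVID-19 Hospitalization/ER visit Adjusted by Covariates", for ITT, PP1 and PP2.

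No other part of the SAP supplies a covariance term or says at which covariate values the adjusted probabilities are evaluated.

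**The concern.** Two predictions from one fitted model are generally correlated, because they use the same estimated covariate coefficients. Adding the squared standard errors treats them as independent, which is right only when the model has no covariate. This section exists for models that have one.

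The p-value comes from the model's treatment contrast, which uses the full covariance matrix, and the CI does not. A reader could therefore see p<0.05 beside an interval that includes 0 because of the formula and not the data. SAP 4.1.6 says the totality of evidence will inform the Phase III decision, and these adjusted estimates are part of that evidence.

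**Working it through.** **Inputs.** From the SAP: 200 and 100 subjects (2.4, 4.1.4), risks of 15% and 30% (4.1.4), two-sided 0.05 (4.1.3). Assumed, because the documents do not give them: covariate prevalence, imbalance between arms, odds ratios (1.5 to 3 for a binary covariate, 1.3 to 2 per SD for a continuous one), and the covariate value at which the probabilities are evaluated.

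**The plan's own figures.** The SAP gives no value for the adjusted SE. Its planning inputs hold together: 0.15 × 186 = 0.30 × 93 = 27.9 events per arm, as 4.1.3 says, and 279 × 1.075 ≈ 300. Exact power at 186/93 is 78.9% for a continuity-corrected chi-square and 80.2% for Fisher, against the stated 80%.

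**Formula.** Take logit p_t(x) = a_t + b·x for arm t and one binary covariate x. Each subject has information weight p(1−p). Let W_t be the total weight in arm t, and m_t the weighted mean of x there. At reference value x*, with η_t = a_t + b·x*:

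- Var(η_t) = 1/W_t + (x* − m_t)²·Var(b)
- Cov(η_1, η_0) = (x* − m_1)(x* − m_0)·Var(b)
- On the probability scale, multiply by d_t² and d_1·d_0 respectively, with d_t = p_t(1−p_t) at x*.
- Correct SE = √(V1 + V0 − 2·Cov). SE as written = √(V1 + V0).

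The covariance is near 0 when x* is close to the arm means. It is positive when x* lies well to one side of both, and negative when x* lies between them.

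**Worked case: 10% prevalence in both arms, odds ratio 2.** Intercepts giving 15% and 30% overall are −1.820 and −0.924, with b = ln 2 = 0.693. Then W_1 = 25.30, m_1 = 0.146, W_0 = 20.77, m_0 = 0.119, Var(b) = 0.1876.

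Equal class weights put x* at 0.5. The adjusted probabilities are 0.1865 and 0.3595, with d_1 = 0.1517 and d_0 = 0.2303.

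- V1 = (1/25.30 + 0.354² × 0.1876) × 0.1517² = 0.00145
- V0 = (1/20.77 + 0.381² × 0.1876) × 0.2303² = 0.00400
- Cov = 0.354 × 0.381 × 0.1876 × 0.1517 × 0.2303 = 0.00088 (correlation 0.37)
- As written: √0.00545 = 0.0738. Correct: √(0.00545 − 0.00177) = 0.0607. Ratio 1.217.

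At the observed margin (x* = 0.1) the covariance is only 0.000004, and the SEs are 0.0524 and 0.0523.

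**Other one-covariate cases (odds ratio 2)**

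| Prevalence, active / placebo | Evaluated at | SE as written | SE with covariance | Ratio |
|---|---|---|---|---|
| 10% / 10% | equal weights | 0.0738 | 0.0607 | 1.217 |
| 10% / 10% | observed margin | 0.0524 | 0.0523 | 1.002 |
| 25% / 25% | equal weights | 0.0587 | 0.0570 | 1.030 |
| 25% / 25% | observed margin | 0.0525 | 0.0523 | 1.004 |
| 60% / 40% | observed margin | 0.0534 | 0.0539 | 0.990 |
| 15% / 5% | equal weights | 0.0751 | 0.0638 | 1.179 |
| 15% / 5% | observed margin | 0.0530 | 0.0535 | 0.991 |

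In the 60% / 40% case x* = 0.533 lies between m_1 = 0.711 and m_0 = 0.471, so the covariance is negative and the interval slightly too narrow.

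**Ranges by simulation (about 2,000 trials per scenario).**

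- A continuous covariate at its mean gives ratios from 0.986 (0.5 SD imbalance, OR 1.3 per SD) to 1.024 (balanced, OR 2 per SD).
- Equal class weights give at most 1.02 for a 50/50 split, 1.02 to 1.05 at 25% prevalence, and 1.19 to 1.27 at 10% (5th to 95th percentile of single trials 1.10 to 1.43).
- If the rule is carried to the four-covariate model, intervals are 1.2% to 1.4% too wide at observed margins. With equal weights they are 1.5%, 3%, 9% and 27% too wide when 50%, 30%, 20% and 10% of subjects fall in the smaller symptom-day class.

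**Effect on reading the result (6,000 trials; 10% prevalence, odds ratio 2)**

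| | SE as written | SE with covariance |
|---|---|---|
| p<0.05 with CI including 0, equal weights | 18% | 2.5% |
| Coverage, equal weights | 97.8% | 94.3% |
| p<0.05 with CI including 0, observed margin | 2.4% | 2.3% |
| Coverage, observed margin | 94.5% | 94.5% |

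**The case against.** The algebra is not in dispute; materiality is. The strongest case against runs as follows.

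- A large error needs a rare class, class coding and equal weights together, and the SAP specifies none of these. At 25% prevalence with equal weights the ratio is only 1.03. This stands. But the SAP does not exclude the combination, and the shell table "Summary of Categorical Demographic Characteristics by Treatment" lists traits that may be uncommon, such as chronic liver disease and age 75 or over.
- That table is descriptive. It gives no prevalences and names no adjustment covariates. Age and BMI are also summarised as continuous, so in the full model only sex and symptom days are evidently categorical. This stands: the 10% case is a conditional extreme, not a forecast.
- The SE rule closes the one-at-a-time paragraph, so using it for the full and stepwise models is inference. The full model is also conditional on 10 events per covariate. This stands: the four-covariate figures describe an implied use.
- Some disagreement would remain with the correct SE, because the test is on the logit scale and the CI on the risk-difference scale. This also stands, at about 2% to 2.5% in the worked case. It does not explain 18%.
- The consequence is low, because superiority rests on the unadjusted chi-square test. This bears on the priority of the correction, not on whether the formula is right.

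**Conclusion.** The concern holds. The formula in SAP 4.1.6 is wrong for the covariate-adjusted models it governs, and nothing else in the SAP corrects it.

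For one covariate at observed means or margins the error is small, from about 1.4% too narrow to 2.4% too wide. It becomes material when an unevenly split class covariate is given equal weights: 19% to 27% too wide at 10% prevalence under the assumed odds ratios.

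The primary chi-square test and its CI are untouched. Where the error is material it is conservative, so it creates no false claim of efficacy. The cost is a supportive interval that may cross 0 for no reason in the data. The correction should be made, but the primary analysis does not depend on it.

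**What to change.** In SAP 4.1.6, replace the SE sentence with a delta-method SE from the full model covariance matrix, √(V1 + V0 − 2·Cov), and state that the same rule applies to the one-at-a-time, full and stepwise models.

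State the reference covariate distribution. The preferred choice is to predict each subject's risk under both arms, average over the observed trial covariates, and use a delta-method or bootstrap SE. Take the adjusted p-value and CI from that same estimate. In draft shell Table 14.2.1.4, correct the p-value footnote, which names an unadjusted test in a table of adjusted results.

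The cost is SAP wording and a few lines of code, with no added data. Adding only the covariance term keeps the present estimand (adjusted probabilities at a fixed covariate value). Averaging over trial subjects changes it, so the choice must be stated before unblinding.
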